### 3.3.2. Benefit Assessment

Participants enrolled into this study are healthy participants. There will be no direct health benefits gained from participation in this study. The participants' involvement will be contributing to the PK analysis and safety profile of GR37547 compared to reference ciprofloxacin tablets.

### 3.3.3. Overall Benefit: Risk Conclusion

Healthy volunteers will not gain any direct health benefit by participating in this study. Measures have been taken to minimise risk to participants in this study.

## 4. OBJECTIVES AND ENDPOINTS

**Table 3 Study Objectives and Endpoints**

Objectives	Endpoints
Primary  To determine if 500 mg Ciprofloxacin (GR37547) tablets are bioequivalent to reference 500 mg Ciprofloxacin tablets in healthy adult participants under fasting conditions.	Plasma PK parameters: $AUC_{(0-t)}$ and $C_{max}$ , for ciprofloxacin in relevant treatments.
Secondary  To assess secondary PK parameters of 500 mg ciprofloxacin tablets (GR37547) relative to reference 500 mg ciprofloxacin in healthy adult participants under fasting conditions .  To compare the safety and tolerability of a single dose of a 500 mg ciprofloxacin tablet (GR37547) with reference 500 mg ciprofloxacin tablet, in healthy adult participants under fasting conditions.	
 
Plasma PK parameters: <math>AUC_{(0-\infty)}</math>, <math>t_{max}</math>, <math>\%AUC_{ex}</math> and <math>t_{1/2}</math> for ciprofloxacin in relevant treatments.
 
Adverse events (AE), clinical laboratory values (Haematology and Biochemistry), ECGs and vital signs
 

$AUC_{(0-\infty)}$ = Area under the concentration-time curve from time zero (pre-dose) extrapolated to infinite time; $\%AUC_{ex}$ = Percentage of $AUC(0-\infty)$ obtained by extrapolation; $AUC_{(0-t)}$ = Area under the plasma concentration versus time curve from time zero to $t$ , where $t$ is the time of the last quantifiable concentration; $t_{1/2}$ = Terminal phase half-life $C_{max}$ = Maximum observed concentration; $T_{max}$ = Time of occurrence of $C_{max}$ .	

[figure not shown]
## 5. STUDY DESIGN

### 5.1. Overall Design

This is a Phase I, open label, balanced, randomised, single dose, two-way crossover study, enrolling approximately 26 healthy participants at a single centre.

Each enrolled study participant will participate in two treatment periods in accordance with the randomisation schedule. The treatment periods will be separated by a washout period of at least 7 days and no more than 14 days.

**Figure 1** Study Schematic

Study participants will be randomised to one of two treatment sequences (A-B or B-A). A single dose of one of the two treatments A or B, will be administered on Day 1, in each treatment period. Each participant will participate in both treatment periods and receive a single dose of each treatment.

Study treatments will be referred to as Test and Reference throughout the protocol:

- **Treatment A – Test: GR37547 (CIPVALTM), ciprofloxacin 500mg tablets.**
- **Treatment B - Reference: Ciproxin, ciprofloxacin 500mg tablets.**

Treatment periods 1 and 2 will be separated by a washout period of 7 to 14 days.

The total duration in the study for each participant is expected to be 5 to 7 weeks, from screening to their last visit.

## 5.2. Number of Participants

Approximately 26 participants will be randomized such that at least 22 evaluable participants complete the study.

Participants who withdraw or are withdrawn from the study will not be replaced, unless fewer complete the study than the estimated number of evaluable participants (see Section 10.1 ).

If a Participant is replaced, the replacement will be allocated the subject number of PPD plus the subject number being replaced (e.g., Subject PPD will be replaced by PPD). The subject numbers being replaced will be selected such that the replacement participants receive the same treatment sequence as the withdrawn participants and the sequence balance is maintained.

## 5.3. Participant and Study Completion

A participant is considered to have completed the study if he/she has completed all phases of the study including the last scheduled procedure shown in the SoA.

The end of the study is defined as the date of the last visit of the last participant in the study or last scheduled procedure shown in the SoA for the last participant in the trial.

## 5.4. Scientific Rationale for Study Design

- This study is a standard single dose fasted BE design.
- This study will assess whether the test formulation is bioequivalent to the reference treatment.
- This is a pivotal study and meets guidelines for all major authorities on BE study design.

## 5.5. Dose Justification

The dose of ciprofloxacin (500 mg) in GR37547 is a well established and approved dose, marketed for the treatment of bacterial infections in adults. This study will be conducted using a single dose of the highest GR37547 ciprofloxacin strength marketed, in keeping with international BE guidelines. [EMEA, 2010].

# 6. STUDY POPULATION

Specific information regarding warnings, precautions, contra-indications, AEs, and other pertinent information on the Test product or other study treatment that may impact participant eligibility is provided in the reference 500 mg ciprofloxacin product information leaflet [CIPROXIN Package Insert, 2016].

Prospective approval of protocol deviations to recruitment and enrolment criteria, also known as protocol waivers or exemptions, is not permitted, as these can potentially jeopardize the scientific integrity of the study, regulatory acceptability or participant safety.

Therefore adherence to inclusion and exclusion criteria as stated in the protocol is essential.

## **6.1. Inclusion Criteria**

Participants are eligible to be included in the study only if all of the following criteria apply:

### **Age**

1. Participant must be between 18 and 60 years of age inclusive, at the time of signing the informed consent.

### **Type of Participant and Disease Characteristics**

2. Healthy, non-smoker, as determined by the investigator or medically qualified designee based on a medical evaluation including medical history, physical examination, laboratory tests, and cardiac monitoring.
3. A participant with a clinical abnormality or laboratory parameter(s) which is/are not specifically listed in the inclusion or exclusion criteria, outside the normal reference range for the population being studied may be included only if the investigator in consultation with the Medical Monitor if required, agree and document that the finding is unlikely to introduce additional risk factors and will not interfere with the study procedures.

### **Weight**

4. Body weight  $\geq$ 50 kilogram (kg) and body mass index (BMI) within the range 19-30kg/m^2(inclusive).

### **Sex**

5. Healthy Male or female participants

#### **a. Male participants:**

A male participant must agree to use contraception as detailed in [Appendix 1](#) of this protocol during the treatment period and for at least 5 days, after the last dose of study treatment and refrain from donating sperm during this period.

#### **b. Female participants:**

A female participant is eligible to participate if she is not pregnant (see [Appendix 1](#)), not breastfeeding, and at least one of the following conditions applies:

- (i) Not a woman of childbearing potential (WOCBP) as defined in [Appendix 1](#)

OR

(ii) A WOCBP who agrees to follow the contraceptive guidance in [Appendix 1](#) [Appendix 5](#) during the treatment period and for at least 30 days after the last dose of study treatment.

The investigator is responsible for ensuring that male and female study participants understand how to correctly use the methods of contraception described in [Appendix 1](#)

### **Informed Consent**

6. Capable of giving signed informed consent as described in [Appendix 2](#) which includes compliance with the requirements and restrictions listed in the informed consent form (ICF) and in this protocol.

## **6.2. Exclusion Criteria**

Participants are excluded from the study if any of the following criteria apply:

### **Medical Conditions**

1. History or presence of cardiovascular, respiratory, hepatic, renal, gastrointestinal, endocrine, haematological, neuromuscular, psychiatric, auto-immune or neurological disorders .
2. History of convulsions.
3. Any other condition that is capable of significantly altering the absorption, metabolism, or elimination of drugs; constituting a risk when taking the study treatment; or interfering with the interpretation of data.
4. History of any malignancies or chemotherapy/radiation within the past 5 years excluding treated squamous carcinoma of the skin and adequately excised basal cell carcinoma
5. History of kidney, heart or lung transplants.
6. History or presence of rheumatoid arthritis.
7. Presence of hypokalaemia where the serum potassium is < lower limit of normal (LLN).
8. Presence of hypomagnesaemia where the serum magnesium is < LLN.
9. Fasting blood glucose  $\geq 7$  mmol/L.
10. Serum glucose-6-phosphate dehydrogenase < LLN.
11. Abnormal renal function, as determined by creatinine clearance and considered as clinically significant by the investigator will be excluded.
12. Alanine transaminase (ALT)  $> 1.5 \times$  upper limit of normal (ULN)

13. Bilirubin  $>1.5 \times \text{ULN}$  (isolated bilirubin  $>1.5 \times \text{ULN}$  is acceptable if bilirubin is fractionated and direct bilirubin  $<35\%$ ).
14. Current or chronic history of liver disease, or known hepatic or biliary abnormalities (with the exception of Gilbert's syndrome or asymptomatic gallstones)
15. Excessive alkalinity of the urine ( $\text{pH} \geq 9$ ), as determined on Day -1.
16. Abnormal blood pressure (BP) as determined by the investigator.
17. QT interval corrected for heart rate according to Bazett's formula ( $\text{QTcB} > 450$  milliseconds (msec)). Participants with a known risk of QT prolongation will be excluded.

NOTES:

- For purposes of data analysis, only  $\text{QTcB}$ , will be used.

### **Prior/Concomitant Therapy**

18. Past or intended use of over-the-counter or prescription medication including herbal medications, within 14 days prior to dosing unless, in the opinion of the investigator and sponsor, the medication will not interfere with the study. Specific medications listed in Section 7.7 may be allowed.

### **Prior/Concurrent Clinical Study Experience**

19. Where participation in the study would result in loss of blood or blood products in excess of 500 mL within 90 days.
20. Exposure to more than 4 new chemical entities within 12 months prior to the first dosing day.
21. Current enrolment or past participation within the last 90 days before signing of consent in this or any other clinical study involving an investigational study treatment.

### **Diagnostic assessments**

22. Presence of Hepatitis B surface antigen (HBsAg) at screening or a Positive Hepatitis C antibody test result at screening.

NOTE: Subjects with positive Hepatitis C antibody due to prior resolved disease can be enrolled, only if a confirmatory negative Hepatitis C RNA test is obtained.

23. Positive pre-study drug/alcohol screen
24. Positive human immunodeficiency virus (HIV) antibody test
25. Regular use of known drugs of abuse

## Other Exclusions

26. Sensitivity to heparin or heparin-induced thrombocytopenia
27. Sensitivity to any of the study treatments, or components thereof, or drug or other allergy including allergy to quinolones that, in the opinion of the investigator or medical monitor, contraindicates participation in the study.
28. Regular alcohol consumption within 6 months prior to the study defined as:
  - An average weekly intake of >21 units for males or >14 units for females. One unit is equivalent to 8 g of alcohol: a half-pint (~240 mL) of beer, 1 glass (125 mL) of wine or 1 (25 mL) measure of spirits.
29. Urinary cotinine levels indicative of smoking or history or regular use of tobacco- or nicotine-containing products within 6 months prior to screening.

## 6.3. Lifestyle Restrictions

- Study participants must avoid direct exposure to sunlight and UV radiation for 24 hrs after dosing, due to potential for photo-toxicity reactions.
- Participants must not drive or operate machinery for 24 hours following the dose of study medication.

### 6.3.1. Meals and Dietary Restrictions

- Refrain from consumption of red wine, Seville oranges, grapefruit or grapefruit juice, pomelos, exotic citrus fruits, grapefruit hybrids, or fruit juices from 7 days prior to the first dose of study medication until after the final dose.
- Participants will be administered the treatment in the fasted state.
- Following an overnight fast of at least 10 hrs, participants should be administered the study drug with 240 mL (8 fluid ounces) of water. No food should be allowed for at least 4 hrs post-dose. Water is allowed as desired except for one hr before and after drug administration. Participants should receive standardized meals scheduled at the same time in each period of the study.
- Adequate hydration must be maintained, whilst taking into consideration the 1 hr water restriction pre-and post study medication dosing.

### 6.3.2. Caffeine, Alcohol, and Tobacco

- During each dosing session, participants will abstain from ingesting caffeine- or xanthine-containing products (e.g., coffee, tea, cola drinks, and chocolate) for 24 hrs before the start of dosing until after collection of the final PK sample.

- During each dosing session, participants will abstain from alcohol for 24 hrs before the start of dosing until after collection of the final PK sample.

### **6.3.3. Activity**

- Participants will abstain from strenuous exercise for 48 hrs before the start of dosing until after collection of the final PK sample, at each dosing session. Participants may participate in light recreational activities during studies (e.g., watching television, reading).

## **6.4. Screen Failures**

Screen failures are defined as participants who consent to participate in the clinical study but are not subsequently randomized in the study. A minimal set of screen failure information is required to ensure transparent reporting of screen failure participants to meet the Consolidated Standards of Reporting Trials (CONSORT) publishing requirements and to respond to queries from regulatory authorities. Minimal information includes demography, screen failure details, eligibility criteria, and any SAEs.

Individuals who do not meet the criteria for participation in this study (screen failure) may not be rescreened.

## **7. TREATMENTS**

Study treatment is defined as any investigational treatment(s), marketed product(s), placebo, or medical device(s) intended to be administered to a study participant according to the study protocol.

## 7.1. Treatments Administered

**Table 4 Study Treatments**

Study Treatment		
	Test Product	Reference Product
Study Treatment Name:	GR37547/Ciprofloxacin 500 mg (CIPVAL™)	Ciproxin
Dosage formulation:	Tablet	Tablet
Unit dose strength(s)/Dosage level(s):	500 mg Ciprofloxacin	
Route of Administration	Route: Oral Duration: single dose	
Dosing instructions:	1 tablet to be taken orally with 240 mL water.	
Physical Description:	White to off white capsule shape with break line on upper side and embossed "GSK500" on lower side.	Nearly white to slightly yellowish film coated oblong tablets with break line and "CIP 500" marked on upper side and "BAYER" on lower side.
Manufacturer /Supplier	GlaxoSmithKline Pakistan Limited, [name].	Bayer Pharma AG/Bayer plc, U.K.

## 7.2. Dose Modification

Not applicable.

## 7.3. Method of Treatment Assignment

Participants will be assigned to one of two sequences (A-B or B-A) in accordance with the randomisation schedule generated by PAREXEL Biostatistics, prior to the start of the study, using validated software. Randomization numbers will be assigned sequentially. Possible replacements will be handled according to Section [5.2](#).

A description of each regimen is provided in [Table 5](#). Treatments administered are as follows:

- Treatment A – Test GR37547 Ciprofloxacin 500 mg tablets (CIPVAL™)
- Treatment B – Reference 500 mg Ciprofloxacin tablets (Ciproxin)

On Day -1, participants will be assigned a unique randomization number. The randomization number encodes the participant's assignment to one of the 2 sequences. On Day 1, each participant will be administered a single dose of open label study treatment. After a washout period of 7-14 days, each participant will be administered a single dose of the other treatment not previously received.

**Table 5 Description of each treatment sequence**

Sequence	Number of Participants Per Group	Treatment Period 1	Treatment Period 2
A-B	13	Treatment A (GR37547)	Treatment B Reference
B-A	13	Treatment B Reference	Treatment A (GR37547)

#### **7.4. Blinding**

This is an open label study; potential bias will be reduced by assigning treatment by randomization.

#### **7.5. Preparation/Handling/Storage/Accountability**

No special preparation of study treatment is required.

- The investigator or designee must confirm appropriate temperature conditions have been maintained during transit for all study treatment received and any discrepancies are reported and resolved before use of the study treatment.
- Only participants enrolled in the study may receive study treatment and only authorized site staff may supply or administer study treatment. All study treatments must be stored in a secure, environmentally controlled, and monitored (manual or automated) area in accordance with the labeled storage conditions with access limited to the investigator and authorized site staff.
- The investigator, institution, or the head of the medical institution (where applicable) is responsible for study treatment accountability, reconciliation, and record maintenance (i.e., receipt, reconciliation, and final disposition records).

- The final disposition of unused study treatment will be handled as per GSK's requirements after study conduct.
- Under normal conditions of handling and administration, study treatment is not expected to pose significant safety risks to site staff.
- A Material Safety Data Sheet (MSDS)/equivalent document describing occupational hazards and recommended handling precautions either will be provided to the investigator, where this is required by local laws, or is available upon request from GSK.

## 7.6. Treatment Compliance

When the individual dose for a participant is prepared from a bulk supply, the preparation of the dose will be confirmed by a second member of the study site staff.

When participants are dosed, they will receive study treatment directly from the investigator or designee, under medical supervision. The date and time of each dose administered in the clinic will be recorded in the source documents. The dose of study treatment and study participant identification will be confirmed at the time of dosing by a member of the study site staff other than the person administering the study treatment. Study site personnel will examine each participant's mouth to ensure that the study treatment was ingested.

## 7.7. Concomitant Therapy

Any medication or vaccine (including over-the-counter or prescription medicines, vitamins, and/or herbal supplements) that the participant is receiving at the time of enrolment or receives during the study must be recorded along with:

- reason for use
- dates of administration including start and end dates
- dosage information including dose and frequency

The ciprofloxacin SMPC [**CIPROXIN** Package Insert, 2016] should be consulted for detailed information regarding interaction with concomitant therapy.

Participants must abstain from taking prescription or non- prescription drugs (including vitamins and dietary or herbal supplements) for 14 days before the start of the study until completion of the follow-up visit, unless, in the opinion of the investigator and sponsor, the medication will not interfere with the study.

Paracetamol, at doses of  $\leq 2$  grams/day, is permitted for use any time during the study. Other concomitant medication may be considered on a case-by-case basis by the investigator in consultation with the Medical Monitor if required. Please refer to the summary of interactions with other medicinal products in the Package Insert for Ciproxin.

## 7.8. Treatment after the End of the Study

This is a study in healthy participants who will not receive any treatment after the end of the study.

## 8. DISCONTINUATION CRITERIA

### 8.1. Discontinuation of Study Treatment

Participants will be permanently withdrawn from study treatment, at the discretion of the investigator in the event of the following medical reasons after receiving the first dose of study medication:

- anaphylaxis,
- sensitivity reactions (e.g. pharyngeal or facial oedema, dyspnoea, rash, severe dermatologic reactions,)
- tendinopathy and tendon rupture
- liver events (see Section 8.1.1).
- positive pregnancy test
- vomiting within 4 hours (approximately  $2 \times$  the median  $t_{max}$ ) of the reference product
- other AEs related to study treatment at the investigator discretion

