### **3.3. Benefit/Risk Assessment**

Ciprofloxacin was first approved as an antibacterial agent by the Medicines and Healthcare Product Regulatory Agency (MHRA), in the United Kingdom (UK) in 1987 [[CIPROXIN Package Insert, 2016](#)]. The safety profile of ciprofloxacin is well established based on clinical trial safety data and unsolicited pharmacovigilance reports. More detailed information about the known and expected benefits and risks and reasonably expected AEs of Ciprofloxacin may be found in the Summary of Product Characteristics (SmPC) [[CIPROXIN Package Insert, 2016](#)].

The following section outlines the risk assessment and mitigation strategy for this protocol.

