**Table 2 Summary of Risks and Mitigation Strategies for Investigational Products**

Potential Risk of Clinical Significance	Summary of Data/Rationale for Risk	Mitigation Strategy
Investigational Product (IP) [GR37547]		
Allergic reactions	
Contraindication: Anaphylaxis and anaphylactic shock which may be life threatening may occur if a volunteer has an allergy to the active substance ciprofloxacin, excipients, or other quinolones. Hypersensitivity reactions have been reported following the first dose. Some reactions reported include cardiovascular collapse, loss of consciousness, tingling, pharyngeal or facial oedema, dyspnoea, urticaria, and itching.
 
Other hypersensitivity reactions include fever, rash, severe dermatologic reactions (e.g. Stevens-Johnson syndrome); vasculitis; arthralgia; myalgia; serum sickness; or allergic pneumonitis.
	
Exclude participants with a known history of hypersensitivity to quinolones, ciprofloxacin, or excipients including cellulose microcrystalline, crospovidone, maize starch, magnesium stearate, silica colloidal anhydrous, hypromellose, macrogol and titanium dioxide.
 
Further doses must be discontinued if a participant develops skin rash, jaundice, or any other sign of hypersensitivity following the study medication, and supportive measures immediately instituted.
 
In the event of serious anaphylactic reactions, epinephrine must be given immediately. Oxygen, intravenous steroids, and airway management, including intubation, should be administered as required.

Potential Risk of Clinical Significance	Summary of Data/Rationale for Risk	Mitigation Strategy

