	
reported.
 
Psychiatric reactions may occur including anxiety, paranoia, depression, confusion, psychoses, hallucinations, depression, nervousness, agitation, insomnia, anxiety, paranoia, nightmares and rarely, suicidal thoughts or acts. Depression or psychotic reactions can progress to suicidal ideations/thoughts and self-injurious behaviour, such as attempted suicide or completed suicide.
 
There have also been very rare cases (<1/10000) of migraine, disturbed coordination, gait disturbance, olfactory nerve disorders, intracranial hypertension and increased intracranial pressure (including pseudotumour cerebri).
	

Potential Risk of Clinical Significance	Summary of Data/Rationale for Risk	Mitigation Strategy
Peripheral Neuropathy	Rare cases of sensory or sensorimotor axonal polyneuropathy affecting small and/or large axons resulting in paresthesias, hypoesthesia, dysesthesias and weakness have been reported in patients receiving quinolones, including ciprofloxacin.	Further ciprofloxacin doses will be discontinued if any participant experiences symptoms of neuropathy including pain, burning, tingling, numbness, and/or weakness, or is found to have deficits in light touch, pain, temperature, position sense, vibratory sensation, and/or motor strength in order to prevent the development of an irreversible condition.
Vision disorders	Warning: Impaired vision such as diplopia and colour distortions may also occur.	Study participants will be advised to immediately report any signs of visual disturbances to the investigator.
Hearing disorders	Precaution: There have been rare cases of tinnitus, or transitory deafness (especially at higher frequencies) with ciprofloxacin.	Study participants will be advised to immediately report any signs of hearing disturbances to the investigator.
Metabolic reactions	
Precaution: Hypoglycaemia can occur in Diabetic patients.
 
Ciprofloxacin may increase the effects of caffeine, and result in caffeine accumulation if consumed concomitantly with quinolones.
	
Only healthy volunteers to be enrolled. Exclude volunteers with known or suspected Diabetes based on history, and investigator discretion following review of fasting blood glucose results.
 
All participants to be advised to avoid caffeine containing food and beverages for 24 hours prior until 24 hours following dosing with ciprofloxacin.

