## 9. STUDY ASSESSMENTS AND PROCEDURES

Study procedures and their timing are summarized in the SoA.

- Protocol waivers or exemptions are not allowed
- Immediate safety concerns should be discussed with the sponsor immediately upon occurrence or awareness to determine if the participant should continue or discontinue study treatment.
- Adherence to the study design requirements, including those specified in the SoA, is essential and required for study conduct.
- All screening evaluations must be completed and reviewed to confirm that potential participants meet all eligibility criteria. The investigator will maintain a screening log to record details of all participants screened and to confirm eligibility or record reasons for screening failure, as applicable. During screening the following will be completed:
  - Demographic parameters will be captured: Year of birth, sex, race and ethnicity.
  - Medical /Medication /family history will be assessed as related to the inclusion/exclusion criteria in Section 6.
- Procedures conducted as part of the participant's routine clinical management (e.g., blood count) and obtained before signing of ICF may be utilized for screening or baseline purposes provided the procedure met the protocol-specified criteria and was performed within the time frame defined in the SoA.
- Blood samples will be collected as per SoA.
  - The maximum amount of blood collected from each participant over the duration of the study, including any extra assessments that may be required, will not exceed 500 mL.
  - Repeat or unscheduled samples may be taken for safety reasons or for technical issues with the samples.
  - Samples will be destroyed within 6 months after the clinical execution of the study has been completed.

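### Section 8.1 leaves withdrawal after a hypersensitivity reaction to investigator discretion and does not name neuropathy, whereas Table 2 requires further ciprofloxacin doses to be stopped for both

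*Combined protocol and SAP*

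**What the plan says.** Section 8.1 opens its list of reasons for stopping with "Participants will be permanently withdrawn from study treatment, at the discretion of the investigator in the event of the following medical reasons". The list covers anaphylaxis, sensitivity reactions (rash is one of the examples), tendon problems, liver events, a positive pregnancy test and early vomiting. It ends with "other AEs related to study treatment at the investigator discretion". Neuropathy appears nowhere in Sections 8.1 to 8.1.3.

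Table 2, in Section 3.3.1, addresses the same events. Section 3.3 introduces it with "The following section outlines the risk assessment and mitigation strategy for this protocol", so it is part of the plan and not only background. For allergic reactions it says "Further doses must be discontinued if a participant develops skin rash, jaundice, or any other sign of hypersensitivity following the study medication". For peripheral neuropathy it says "Further ciprofloxacin doses will be discontinued if any participant experiences symptoms of neuropathy including pain, burning, tingling, numbness, and/or weakness", extends this to sensory or motor deficits found on examination, and gives the reason: "in order to prevent the development of an irreversible condition". Neither row mentions discretion.

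**The concern.** Each participant takes one tablet of each product, 7 to 14 days apart, and both are ciprofloxacin 500 mg. For anyone who reacts to the first dose, the second is a re-challenge with the same drug. Section 3.3.2 states that participants gain no direct health benefit. Table 2 describes anaphylaxis as possibly life-threatening and notes "Hypersensitivity reactions have been reported following the first dose".

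One part of the protocol requires a stop for these events. The part headed as the discontinuation rule appears to leave the stop to judgement for hypersensitivity, and for neuropathy offers only a general item on other adverse events. The realistic cases are a mild rash or transient tingling after dose 1, where an investigator reading only Section 8.1 might think dosing could go ahead. What is at stake is participant safety and the clarity of the rule. No PK estimate or test depends on it.

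**Working it through.** **Step 1: the two rules side by side.**

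| Event after dose 1 | Table 2 (Section 3.3.1) | Section 8.1 |
|---|---|---|
| Anaphylaxis, rash, other sensitivity reaction | Stop is mandatory | Listed, under a lead-in that refers to investigator discretion |
| Jaundice as a sign of hypersensitivity | Stop is mandatory | Not named under sensitivity reactions |
| Neuropathy symptoms or deficits | Stop is mandatory | Not named; reachable only through the last item, which needs a judgement of relatedness and then discretion |

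**Step 2: is the difference in wording meaningful?** Table 2 states discretion where it is wanted: its hepatobiliary row leaves stopping for rises above the upper limit of normal to the principal investigator. The allergy and neuropathy rows have no such clause. Section 8 can also write a firm stop: under Section 8.1.2 a participant who meets a QTc criterion is withdrawn, with no discretion clause. The protocol therefore uses both forms, and Section 8.1 uses the softer one for anaphylaxis.

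**Step 3: does another section settle it?**
- Section 9 sends immediate safety concerns to the sponsor "to determine if the participant should continue or discontinue study treatment". That is a discussion, not a stop.
- Section 9.2.3 refers back to Section 3.3.1, but only for the follow-up of adverse events.
- Table 1 marks eligibility criteria at Day -1 under a column covering both periods, so a Period 2 check is a plausible reading. The row's note ties the recheck to randomisation, which occurs in Period 1 only, but the note is visibly incomplete. Even with a Period 2 check, the exclusions in Section 6.2 set no firm stop here. Criterion 1 names disorders, not symptoms. Criterion 3 turns on whether a condition poses a risk. Criterion 27 contains an opinion clause whose reach is unclear.

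No text says which rule prevails.

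**Step 4: what would a firm stop cost in power?** Inputs from Section 10.1: within-participant CV 18%, true ratio 0.95, limits 0.80 to 1.25, one-sided alpha 0.05, one parameter. Planned enrolment is 26, with 22 evaluable needed.

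- Log-scale SD: σ = √ln(1 + 0.18²) = 0.1786.
- Standard error of the treatment difference: SE = σ·√[½(1/n₁ + 1/n₂)], with n₁ + n₂ − 2 degrees of freedom.
- TOST power is integrated over the chi-square distribution of the residual variance.

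| Completers (by sequence) | SE | Power |
|---|---|---|
| 22 (11+11) | 0.0538 | 92.4% |
| 23 (11+12) | 0.0527 | 93.4% |
| 24 (12+12) | 0.0515 | 94.3% |
| 25 (12+13) | 0.0505 | 95.1% |
| 26 (13+13) | 0.0495 | 95.8% |
| 22 (9+13, all losses in one sequence) | 0.0548 | 91.6% |

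The first row agrees with the plan's claim that 22 evaluable participants give 90% power. The margin is 26 − 22 = 4, or 4/26 = 15.4%. One participant stopped after dose 1 costs 95.8 − 95.1 = 0.7 percentage points. Using the whole margin still leaves power above 90%.

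**The case against.** The strongest reply is that the two texts can be obeyed together. Section 8.1 allows withdrawal and Table 2 demands it, so stopping satisfies both and only re-dosing breaches one. Section 8.1 also says participants will be withdrawn, and its last item repeats the reference to discretion, which would be redundant if the lead-in already made every item optional. Two other listed items have firm rules elsewhere: liver events in Section 8.1.1 and pregnancy in Appendix 1. On that view, discretion covers only whether a listed event has occurred.

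Much of this stands. A reader might infer that the protocol permits re-dosing after anaphylaxis, or that no safeguard exists. The documents do not support either inference: Table 2 forbids the second dose, eligibility waivers are barred (Sections 6 and 9), and Day -1 of each period includes an abbreviated physical examination and a review of medical conditions.

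What does not stand is the conclusion that nothing needs changing. If discretion covers only recognition of the event, the sentence is ambiguous and should say so. That reading also does nothing for neuropathy, which Section 8.1 does not name.

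**Conclusion.** The point holds as a mismatch between two safety rules. Section 8.1 is weaker than Table 2, or at best ambiguous, for hypersensitivity, and silent by name on neuropathy. It is not a missing safeguard.

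The weight is minor to moderate. It matters only for a participant with such an event after dose 1, and only one further dose is in question. The documents give no rate for hypersensitivity or rash and call neuropathy rare without a figure, so no event probability can be computed. Section 3.3.1 expects lower risk in healthy volunteers after a single dose than in chronic use. Against that, the possible harms are serious and the correction costs almost nothing.

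The power figures rest on the plan's own assumptions for one parameter. They show that a firm stop is affordable; they do not measure the safety risk. It would also be wrong to infer that liver stopping shares this defect. Section 8.1.1 has one sentence asking the investigator to consider stopping, but it then states that treatment will be discontinued if the stopping criteria are met.

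**What to change.** Split the lead-in of Section 8.1 into a mandatory list and a discretionary list.

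- **Mandatory, with the discretion clause removed:** anaphylaxis or any sign of hypersensitivity, including rash or jaundice; and neuropathy symptoms or deficits, using Table 2's own wording.
- **Cannula pain:** Table 2 expects some pain at the cannula site and also lists pain among the neuropathy symptoms. If the sponsor wants to exclude pain clearly due to the cannula, make the same change in Table 2. Adding an investigator judgement to Section 8.1 alone would create a new mismatch.
- **Liver events:** leave these to Section 8.1.1.

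The change needs no new visits, procedures or analyses. The downside is that a participant stopped after dose 1 leaves the PK population, which under Table 6 takes only those who complete the study with primary parameters for all periods. The margin of 4 covers an occasional loss, and Section 5.2 allows replacement if fewer than 22 complete.
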